Yet, in spite of the high stakes for public health, the comparative risk/benefit ratio of antidepressants is entirely unstudied in older adults with TRD. This stands in contrast with numerous studies in younger adults.²⁵⁻²⁹ This evidence gap was highlighted in critical reviews^{30,31}

that found a complete lack of evidence in this age group. The sole exception is our recent randomized controlled trial (RCT) of aripiprazole augmentation in older adults.^{2,32}

C Study Objectives

The study aims to close the evidence gap on late-life depression in three ways:

C1 Aim 1: Effectiveness

Examine the comparative benefits and risks of antidepressant strategies (augmentation and switching) in older adults with TRD.

Effectiveness outcomes: psychological well-being and remission from depression Safety outcomes: serious adverse events, falls, and fall-related injuries

C2 Aim 2: Effects of Aging

Explore how age, and age-related variables (medical comorbidity, cognitive problems) change the balance of benefits vs. risks.

C3 Aim 3: Maximize Stakeholder Engagement

We will maximize stakeholder engagement to ensure relevancy to providers and patients alike.

C4 Rationale for the Selection of Outcome Measures

OUTCOME	WHEN AND HOW MEASURED	RATIONALE
Psychological well-being is the patient-centered effectiveness outcome (Hypothesis 1a [H1a]).	In Acute, beginning and end of Step 1 (and Step 2); in Continuation months 4, 8, 12.	Psychological well-being encompasses satisfaction, happiness, cognitive engagement,
Secondary quality of life measures are self-reported physical function and social participation.	Measured by NIH Toolbox* (Psychological Well-being) and PROMIS* (Physical function, Social participation). Assessed by independent rater**	and meaning/purpose. It is a critical dimension of quality of life, recommended by patient stakeholders in focus groups as an outcome that matters.
Remission is our clinician- focused effectiveness outcome (H1b): reduction of depressive symptoms below a threshold (MADRS≤10). This goal of treatment is a consensus among practitioners. ^{53,54}	In Acute, beginning and end of Step 1 (and Step 2); in Continuation, months 4, 8, 12 Assessed by independent (blind) rater** via 20-30 minute phone interview.	The MADRS measures 10 areas of depressive symptoms. It is a standard outcome in antidepressant studies. Patient stakeholders described this assessment as "very important" for assessing effectiveness.

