Study sites will be responsible for developing their site-specific recruitment plans and obtaining IRB approval for the plan and all recruitment materials. In most cases, recruitment will be facilitated through partnerships with community mental health and primary care clinics. Plans for recruitment by referral or via a partial waiver of HIPAA authorization for recruitment purposes must be agreed upon by the appropriate community personnel, and approved by the local IRB, prior to implementing.

1.g Randomization Method and Blinding

Randomization of participants will be implemented in REDCap, using a randomized block design within clinic and age group using variable block size, stratified by institutional site and age strata.

Only assessors of outcome measures will be blinded. Participants, providers, and other research staff will not be blinded to participants' condition.

In this pragmatic design where all levels of adherence are allowed, participants will be considered randomized assuming they meet the eligibility requirements at screening (including any safety screens as applicable) and they and/or their clinician has been given a randomization assignment.

1.h Potential Risks

Study Instruments and measures: The assessments to be conducted as part of this study involving mood assessments, neuropsychological testing, and behavioral and functional assessments are non-invasive and carry with them no more than minimal risk. The most significant risks to the participants related to assessments are those that would follow a breach of confidentiality and the disclosure of clinical information. We also include discomfort in the potential risks. The instruments to be used in this study are brief and pragmatic and have been well-tolerated by older adults in other studies.

Aripiprazole: The most common side effect of aripiprazole (occur in 25% of people) is akathisia.

Common side effects (occur in 1-25% of people) include restlessness, insomnia, fatigue, blurred vision, somnolence, tremor, constipation, sedation, and dizziness. There is a potential that aripiprazole may increase the risk of hyperglycemia (increased blood sugar), diabetes, abnormal cholesterol or increased triglycerides.

We will monitor patients for these symptoms and require that they have a fasting blood glucose and lipid profile obtained prior to start of aripiprazole and as often as clinically necessary.

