Neuroleptic malignant syndrome (NMS) has been reported for all atypical antipsychotics, including aripiprazole (albeit rarely -- only 14 cases have been reported, and the aripiprazole dose in these was higher than what is used in this study). Patients who develop this syndrome may have high fevers, muscle rigidity, altered mental status, irregular pulse or blood pressure, rapid heart rate, excessive sweating, and heart arrhythmias.

Bupropion: The most frequent (occurs in more than 25% of people) side effects of bupropion include agitation, dry mouth, and headache. Common side effects (occurs in 1-25% of people) include excessive sweating, dizziness, tremor, constipation, nausea, decreased appetite, weight loss, rash, heart pounding, high blood pressure, unsteadiness when walking, confusion, anxiety, increased urination, and difficulty sleeping. Seizures may occur in patients receiving bupropion; however, at the dose range (max 300mg) and once-daily formulation used in this study, only 2 cases of seizures have been reported, and our exclusion of individuals with seizure disorders will minimize this risk. There is a rare (<1%) risk of mania or hypomania associated with antidepressant treatment.

Lithium: Likely side effects (occurs in more than 25% of people) of lithium carbonate include shakiness of the hands, drowsiness, headache, increased urination, increased thirst, and dry mouth. Common side effects (occurs in 1-25% of people) include weight gain, nausea, vomiting, and diarrhea. These are temporary side effects that will usually stop after the body adjusts over 1-2 weeks. Lithium may commonly slow down the functioning of the thyroid hormone (hormone that controls growth and ability to burn energy) and, after years of treatment, it may affects (occurs in less than 1% of people) the functioning of the kidneys. In rare cases, lithium intoxication may occur with muscular weakness and lack of coordination, confusion, altered consciousness. These risks are less likely at the lower serum levels used in this study.

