NIH Toolbox Cognition and Motor batteries -@done if participant able to be seen in person		х						Х						х			х
Cognition battery including Attention/exec function (flanker and dimsional change card sort), Episodic memory (Picture seq memory), working memory (List sorting), Processing speed (pattern comparison). Baseline only: Language (Oral reading recognition) Motor battery including Dexterity (pegboard), Strength (using grip dynamometer), Balance,																	
gait speed																	
Psychological well-being (NIH Toolbox self-report measure)		х						х						х	X	х	х
Physical Function (PROMIS)		х						х						х	Х	х	х
Social Participation (PROMIS)		х						х						х	Х	х	x
AE and SAE collection (collected anytime the event occurs)																	
Anxiety (PROMIS)		х															
Done by central rater pool at WU by phone:																	
MADRS		х						х						х	х	х	х
*Typically Week 10; or upon dropout																	
**Central rater pool will assess side effects, falls, and adherence during continuation; local s	ites can do	additional	decisi	on sup	ort cal	lls "as n	eeded	during"	this tim	ne							

F3 Baseline

- Participant signs (or returns signed) informed consent form; all elements of informed consent have been discussed and participants' questions answered.
- Local Research Team Assessments: (in person if possible; approximately 3 hours)
 - MINI MDD & Bipolar Modules
 - PHQ-9 (If more than 7 days has elapsed since the PHQ-9 was done at pre-screen.)
 - Suicide History, Risk & Protective Factors
 - Baseline Side Effects
 - Expectations for Adherence
 - Behavioral Therapy Assessment
 - Falls & Related Injuries (history)
 - Height and Weight (self-reported)
 - If indicated by pre-screen: DAST-10
 - o If indicated by pre-screen: AUDIT
 - NIH Toolbox Psychological Well Being
 - o PROMIS Physical Function
 - o PROMIS Social Participation
 - PROMIS Anxiety
 - NIH Cognition and Motor Batteries (in person assessments may be foregone for participants living in remote locations)
 - o ATHF
 - o CIRS-G
 - Medical Conditions and Medication List (study doctor to review before randomization)
 - Confirm inclusion/ exclusion criteria are met
 - Randomize participant; provide initial decision support per randomization status to participant's doctor.
- Central Rater Assessments (by phone; approximately 30 minutes)
 - o MADRS

F4 Decision Support Calls

- Every 2 Weeks During Acute Treatment: Step 1 Weeks 2, 4, 6, 8, 10* & Step 2 Weeks 2, 4, 6, 8, 10*

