- Phone Call with Local Research Team (approximately 10 minutes)
 - o PHQ-9
 - Spontaneous side effect report & severity
 - Falls Assessment
 - Adherence
 - o Counselling about adherence and management of side effects.
 - AE reports done as needed.
 - Decision support staff contact study MDs when needed (e.g. if confusion about whether to increase antidepressant dose).
 - Decision support staff contact participant's clinical provider with recommendations;
 also will typically tell patient the recommendations.

F5 Acute Phase End Assessments

- Step 1 Week 10, Step 2 Week 10, or upon early withdrawal (if possible)
 - If there is a long delay between the Step 1 Week 10 assessment and the initiation of Step 2, the participant may be asked to repeat some or all of the Step 1 End assessments.
- *In addition to Decision Support assessments, local research team will conduct the following assessments (in person if possible; approximately 1 ½ hour):
 - NIH Toolbox Psychological Well Being (may be conducted via phone or Redcap survey)
 - PROMIS Physical Function (may be conducted via phone or Redcap survey)
 - o PROMIS Social Participation (may be conducted via phone or Redcap survey)
 - NIH Cognition and Motor Batteries (may be foregone for participants living in remote locations)
 - Weight (self-reported)
- Central Rater Assessments (by phone; approximately 30 minutes. WU participants may do in person or by phone)
 - o MADRS

F6 Continuation Assessments

- Months 4, 8, and 12 after completing acute treatment in Step 1 and/or 2 as indicated.
- Participants who relapse in Continuation after Step 1 may be invited to participate in Step 2; and then continuation subsequently.
- Local Research Team Assessments (in person if possible; approximately 1½ hour)::
 - NIH Toolbox Psychological Well Being (may be conducted via phone or Redcap survey)
 - PROMIS Physical Function (may be conducted via phone or Redcap survey)
 - o PROMIS Social Participation
 - Weight
 - NIH Cognition and Motor Batteries (Month 12 only; may be foregone for participants living in remote locations)
- Central Rater Assessments (by phone; approximately 30 minutes)
 - o MADRS
 - Falls & Related Injuries
 - Spontaneous side effects and severity(discuss with local sites if needed)
 - Adherence

F7 Genetic Testing

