6.1.2. Outcome measurements

H1a outcome will be measured by NIH Toolbox (Psychological Well-being), and the secondary outcome will be measured by PROMIS (Physical function, Social participation).

H1b outcome will be assessed by independent (blind) raters via phone interview to assess the MADRS score.

H2a outcome will be measured when SAE occurs.

H2b outcome will be assessed by independent raters.

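### Protocol F5 lets the step-end MADRS be rated in person at the coordinating site only, against the blind phone rating in C4, F2 and SAP 6.1.2, leaving a possible but unquantified masking risk for remission at that site

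*Protocol*

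**What the plan says.** Protocol F5 (Acute Phase End Assessments) has the central MADRS done by phone, then adds an exception for one site: "WU participants may do in person or by phone". It applies to Step 1 and Step 2 ends and to early withdrawals.

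The other descriptions of the central rating carry no exception. The outcome table in Protocol C4 reads "Assessed by independent (blind) rater via 20-30 minute phone interview". The schedule in Protocol F2 lists the MADRS under "Done by central rater pool at WU by phone". Protocol F3 (baseline) and F6 (continuation) both use "Central Rater Assessments (by phone; approximately 30 minutes" and stop there. SAP 6.1.2 says "H1b outcome will be assessed by independent (blind) raters via phone interview to assess the MADRS score".

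On masking, Protocol D2 1.g says "Only assessors of outcome measures will be blinded". SAP 3.2 repeats this and gives the safeguard: raters do not ask about treatment and participants are told not to reveal it. Neither document says that rating mode is recorded or examined.

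On signs a rater might see, Protocol D2 1.h says "The most common side effect of aripiprazole (occur in 25% of people) is akathisia", and the likely effects "of lithium carbonate include shakiness of the hands", in more than 25% of people.

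**The concern.** Participants, treating physicians and local staff all know the assignment, so the rater's blind is the only masking in the trial. SAP 6.1.1 lists remission as a primary effectiveness outcome alongside well-being, and it turns on one clinician-rated score against a cut-off.

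A phone rating hides what a participant looks like. A rating in the same room does not, and an instruction not to talk about treatment does nothing about visible signs. If such signs are commoner in one arm, raters at one site could guess that arm more often at the visit that fixes the endpoint. Mode is also chosen after randomization, and F5 covers people who stop early for tolerability, so the choice itself could depend on arm.

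At that site a participant may also be rated by phone at baseline and in person at the end.

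**Working it through.** **1. Mode of the central MADRS, section by section**

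| Place | Time point | Mode | Site exception |
|---|---|---|---|
| Protocol C4 | all | phone, blind | none |
| Protocol F2 | all | phone | none |
| Protocol F3 | baseline | phone | none |
| Protocol F5 | step end | phone | coordinating site: in person allowed |
| Protocol F6 | months 4, 8, 12 | phone | none |
| SAP 6.1.2 | not limited | phone, blind | none |

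F5 is the only outlier, and it concerns only the visit used for remission.

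**2. Which outcome each mechanism reaches**

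SAP 2.2.2 defines remission as MADRS ≤10 at step end. The baseline rating does not enter it, so the change of mode between visits cannot act on remission; unmasking at step end can. MADRS change and 50% response (SAP 6.1.1, secondary) use both ratings, so the mode change can act there.

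**3. What the design already removes**

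Randomization is stratified by site (Protocol D2 1.g, SAP 3.2) and site is a stratum in all analyses (SAP 6.2). A mode effect common to all arms at one site therefore largely cancels between arms. What remains is arm-differential: unmasking, or a choice of mode that depends on arm.

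**4. Which listed signs could separate arms (Protocol D2 1.h)**

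- Step 1: akathisia is listed for aripiprazole and not for bupropion. Tremor is listed for both drugs. Agitation is listed for bupropion in more than 25%.
- Step 2: hand shakiness is listed for lithium and not for nortriptyline, but Protocol E 1.e counts it among effects that usually stop within 1–2 weeks, well before Week 10.

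Akathisia is thus the main candidate.

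**5. The plan's own remission figures**

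Inputs (Protocol H2): 40% remission; Step 1 with 500 per arm at α = 0.05/3; Step 2 with 400 per arm at α = 0.05. I take the tests as two-sided. With p̄ the mean of p₁ = 0.40 and p₂ = 0.40 + d, solve for d in

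power = Φ{[d − z·√(2p̄(1−p̄)/n)] / √([p₁(1−p₁) + p₂(1−p₂)]/n)}, where z is the two-sided critical value.

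| | 80% power | stated | 90% power | stated |
|---|---|---|---|---|
| Step 1 | 10.17 | 10.2 | 11.55 | 11.5 |
| Step 2 | 9.84 | 9.8 | 11.39 | 11.4 |

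All agree within 0.05 point. The point does not depend on them; they serve as a yardstick.

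**6. Scale only, on assumptions the documents do not give**

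Let s be the coordinating site's share of Step 1, with all its step-end ratings in person, and b the arm-differential bias in remission there. Overall shift = s × b. The planned share is 300/1,500 = 20% (Protocol D1); 10% and 30% bracket it.

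| b (points) | s = 10% | s = 20% | s = 30% |
|---|---|---|---|
| 5 | 0.5 | 1.0 | 1.5 |
| 10 | 1.0 | 2.0 | 3.0 |
| 20 | 2.0 | 4.0 | 6.0 |

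At s = 20%, the shifts are 1.0/10.2 = 10%, 2.0/10.2 = 20% and 4.0/10.2 = 39% of the Step 1 detectable difference.

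SAP 3.3 replaces 1,500 by 708, of whom 123 entered Step 2 directly. That leaves 708 − 123 = 585 in Step 1, or 195 per arm if equal. The site's share of these is not given. With fewer per arm the detectable difference exceeds 10.2, so the same shift would be a smaller fraction of it.

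**The case against.** The strongest reply is that this is a wording conflict with no demonstrated bias. Much of that stands.

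- **Drug-specific signs.** A reader might infer that raters would identify a quarter of aripiprazole participants and more than a quarter of lithium participants. The documents do not support this. Both figures are occurrence at any time, not prevalence at step end. Lithium shakiness is described as usually short-lived. Side effects are reviewed every two weeks (Protocol E 1.a). Two of the three Step 1 arms receive bupropion, with its own agitation and tremor, so a restless participant is not clearly marked as an aripiprazole participant.
- **Mode change.** A reader might infer that switching from phone to in-person rating biases remission. It does not enter the definition, and a shift common to all arms largely cancels.
- **A size in MADRS points.** One might compute 0.20 × 0.25 × 2 to 4 points = 0.1 to 0.2 points and call it the trial-wide effect. That product is the shift in one arm's mean, not in a remission proportion. The 2–4 points have no source in the documents, and the 20% is the superseded plan.
- **Permissive wording.** F5 allows in-person rating but does not require it, so the number of such ratings may be small.
- **Well-being.** SAP 4.1 calls H1a the primary hypothesis. It is self-reported and is not touched.
- **Timing.** The design figure in Protocol D1 was updated after the study ended, and a footnote to SAP 4.3 refers to effectiveness analyses already under way. Editing F5 changes no rating already made.

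The conflict itself, and the fact that the safeguard covers only speech, survive these points. Site stratification does not remove an arm-differential effect. Since recording of mode is not mentioned, the plan as written cannot show how often the option was used.

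The point concerns central ratings only. SAP 6.3 accepts a locally administered MADRS when the central one is missing, without stating its mode or masking. That is a separate gap, affecting all sites.

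**Conclusion.** The point holds as a minor one. F5 contradicts C4, F2 and SAP 6.1.2 on how the blinded MADRS is obtained, and departs from the phone-only ratings in F3 and F6. It weakens the trial's only masking, at one site, at the visit that decides remission.

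The consequence is a possible arm-differential unmasking, chiefly through akathisia on aripiprazole. Its size is unknown: it depends on how many ratings were in person, how often signs were present and recognised, and how far a rater's score would move, and the documents give none of these. A shift of 1 to 4 remission points follows only if the site holds 20% of Step 1, all its step-end ratings are in person, and the bias there is 5 to 20 points. The documents do not show that unmasking occurred or that remission is biased.

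For the secondary MADRS change and response outcomes, the mode change matters only to the extent that it differs by arm.

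**What to change.** Delete the in-person option from F5, so that all central MADRS ratings at all sites and visits are by phone, in line with C4, F2 and SAP 6.1.2. Record the mode of each rating. This costs one clause and one data field; the central pool already rates by phone.

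If in-person ratings have already occurred, report their number by arm and step, or state that mode was not captured. Then repeat H1b omitting the whole coordinating site. Site is a randomization stratum, so the comparison among the remaining sites stays randomized, and the run is possible even if mode was never recorded. Do not omit individual in-person ratings instead: that selects on a choice made after randomization, which may depend on arm or tolerability.

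The cost is one sensitivity run with some lost precision. On the planned numbers, dropping 300 of 1,500 leaves 1,200, or 400 per arm. Standard errors grow by √(1,500/1,200) = 1.12, and the Step 1 detectable difference in remission rises from 10.17 to 11.38 points at 80% power and from 11.55 to 12.92 at 90%. The last figure matches the 13 points that Protocol H2 states for 400 per group. The loss in the revised sample depends on the site's actual share, which is not given.

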A priori, specific plans for data analysis correspond to major aims and will be directed by Co-I [name], professor of biostatistics at the coordinating site.

We will follow the intention-to-treat (ITT) principle. In other words, patients who receive coprescribed medications stop randomized medication, or switch to a different medication will continue to be followed. To confirm that ITT findings represent the "true" data on effectiveness, safety, and tolerability of management strategies, we will conduct a sensitivity analysis that will compare ITT to per-protocol findings.

H1a (Psychological Well-Being): We will use a repeated measures 2*2*3 ANOVA with age (60-70, >70), time (baseline, end of Active phase of Step 1) by treatment group (3 levels). Specific time* treatment group contrasts will compare the changes across pairs of treatment groups. These tests will be conducted with a significance level of .05/3. We will include site as a strata in all analyses. For those who proceed to Step 2, analogous repeated measures 2*2*2 ANOVA will be used with a significance level of .05 for the time*treatment group comparison.

H1b (remission): Corresponding 2*3 (age by treatment group) generalized linear models with a logit link function will be computed for the dichotomous outcome of remission.

In the **continuation phase** we will explore the long-term effectiveness of antidepressants: We will test for preservation of psychological well-being and other quality of life variables, and sustained resolution of depressive symptoms, by mixed effects repeated measures models.

We will also test for sustained remission by measuring relapse in each arm. Relapse will be defined as meeting DSM 5 criteria for a major depressive episode, as determined by an Independent Evaluator who will confirm the diagnosis by conferring with a study investigator. We will carry out Cox models examining time to relapse and time to dropout, to examine for treatment inferiority (i.e., whether one antidepressant strategy produces poorer long-term outcomes). Based on our prior research we don't have an empirical basis to posit a specific arm as inferior. Therefore, although these analyses are important to our stakeholders, we describe them as exploratory.

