We will also examine **exploratory hypotheses**, such as whether there are baseline covariates which will help to significantly enhance the prediction of response to treatments, e.g., gender, race, treatment site (primary care vs. specialty clinic), social support, co-treatments. This will enhance the precision medicine implications of the study.

H2: serious adverse events, falls, and fall-related injuries are the safety outcomes. Cox models examining time to event (with Anderson & Gill⁶⁴ extensions for repeated events) will compare the treatment arms during both the acute phase and the continuation in terms of serious adverse events, falls, and fall-related injuries.

We will also compute rates of side effects in each arm, as specifically recommended by patient stakeholders. These data are not hypothesis-testing, but they support the patient-centered goal of allowing clinicians and patients to know what to expect in terms of side effects from treatment.

H3: Moderator analyses (Heterogeneity of Treatment Effects).

Confirmatory analysis (HT-1): Effectiveness and safety differences between treatment arms will be moderated by age. Specifically, with increasing age effectiveness differences between treatment arms will decrease, and safety differences between treatment arms will increase.

Rationale: Our stakeholders demand that we move past the current "one size fits all" paradigm of antidepressant prescribing. Precision treatment would greatly improve older adults' quality of life.

Data analysis plan for moderator testing: We will include the treatment by age group (<70 vs >70) by time interaction to the linear models described above to test for both the benefits and risks for the treatment alternatives.

We are well-powered for a confirmatory moderator analysis examining how age modulates the differences between treatment arms in comparative benefits and risks, because of our recruitment strategy aiming for equally-sized strata of ages (60-70 and >70). Age will be treated as a categorical variable, comparing relative benefits and risks of antidepressants in those aged <70 to those aged >70.

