Here are some scenarios of the types of treatment modulators by age that we will be able to detect with a power > 85% (using SAS's GLMPOWER): (1) If treatment arm A has superior effectiveness over arm B by 2.3 points more than what would be predicted based on age and treatment effects on Psychological Well-being for age 60-70 but no difference between arms for age >70; (2) If treatment arm A has a superior effectiveness over arm B in terms of 13% higher remission rate for age 60-70, but there is no difference between arms for age>70.

Exploratory moderator analyses based on aging-related brain and systemic health variables: Our next step will be to analyze three aging-related variables –impairment in executive cognitive function, frailty, and medical complexity – treated both as continuous variables and categorical variables, using the same models as with chronological age.

Finally, we will examine the relative strength of these moderator variables by performing a combined moderator test.^{76,77} This exploratory analysis incorporates all of the age-related variables into models of each effectiveness and safety finding from hypothesis-testing.

Notes regarding these Heterogeneity of Treatment Effect (moderator) analyses: We will perform statistical contrasts between treatment arms as a function of thee pre-specified moderator variables, and we will report all of these prespecified analyses, as well as post-hoc analyses, in published reports.

H2 Sample Size Determination and Power

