6.2. Analysis methods

To test hypothesis H1a (psychological well-being), a repeated measure of 2*2*3 ANOVA with age (60 – 70, > 70), time (baseline, end of Active phase of Step 1) by treatment group (3 levels) will be used. Specific time * treatment group contrasts will compare the changes across pairs of treatment groups. These tests will be conducted with a Hochberg Step-down procedure. If the comparison with the lowest p-value < 0.05/3 it is significant. If the second lowest p-value is also < 0.05/2 then it also will be significant and if the third p-value is < 0.05 then it also will be significant. We will include site as strata in all analyses. For those who proceed to Step 2, analogous repeated measures 2*2*2 ANOVA will be used with a significance level of .05 for the time*treatment group comparison.

To test hypothesis H1b (remission), a corresponding 2*3 (age by treatment group) generalized linear models with a logit link function will be computed for the dichotomous outcome of remission. Pairwise treatment groups will be compared as in H1a.

To test hypothesis H2a (serious adverse events), Cox models will be used to examine time to event (with Anderson & Grill extensions for repeated events) will compare the treatment arms during both the acute phase and the continuation in terms of serious adverse events. Pairwise comparison between treatment groups will be tested.

To test hypothesis H2b (falls and fall-related injuries), a repeated measures generalized linear model with a cumulative logistic link function. The factors will be treatment group and time (week 2, 4, 6, 8 or 10). The age group (<70 vs.>70) and clinic stratification variables will be included in the model as well as the fall history obtained at baseline. Pairwise comparisons between the treatment group pairs will be formally tested. The same model with a simple logistic link function will be conducted during each 2-week period where the response is a fall-related injury or not.

In terms of the exploratory hypothesis 3, we will include the treatment by age group (<70 vs >70) by time interaction to the linear models described above to test for both the benefits and risks for the treatment alternatives. Additionally, we will fit a model with age as a continuous variable.

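### HT-1 never declares a scale: for remission, SAEs and falls the planned age interaction is a ratio of odds or hazard ratios, which need not track how the absolute arm difference changes with age

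*Protocol*

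**What the plan says.** Protocol section H1 (paragraph H3, moderator analyses) states HT-1: "with increasing age effectiveness differences between treatment arms will decrease, and safety differences between treatment arms will increase". SAP 2.2.2 repeats it but labels it exploratory, where the Protocol calls it confirmatory. The same Protocol paragraph also describes the analysis as "comparing relative benefits and risks of antidepressants in those aged <70 to those aged >70".

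The test in the Protocol is: "We will include the treatment by age group (<70 vs >70) by time interaction to the linear models described above". SAP 6.2 says the same, covers both benefits and risks, and adds a model with continuous age.

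The models this refers back to are:
- Well-being (H1a): repeated-measures ANOVA, which is linear.
- Remission (H1b): "generalized linear models with a logit link function will be computed for the dichotomous outcome of remission"; the SAP uses the same model.
- SAEs (H2a): "Cox models examining time to event", with an extension for repeated events, in both documents.
- Falls and injuries (H2b): Cox in the Protocol. SAP 6.2 uses "a repeated measures generalized linear model with a cumulative logistic link function" for falls and a simple logit for injuries.

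The Protocol gives two HT-1 power scenarios: 2.3 points on well-being, and "13% higher remission rate for age 60-70, but there is no difference between arms for age>70". There is none for SAEs, falls or injuries. Their absolute increases in the power table (section H2) are for main effects.

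Neither document plans an age-specific risk difference. SAP 3.4 promises confidence intervals for differences, but only in general terms.

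**The concern.** In a logit or Cox model the treatment-by-age coefficient is the log of a ratio of odds or hazard ratios. If older participants have a higher baseline risk, a constant ratio produces a larger absolute excess in them while the coefficient is zero. A constant absolute excess produces a non-zero coefficient.

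Aim 2 is about how age shifts the balance of benefit against risk. Weighing remissions against SAEs and falls needs a common unit, such as events per 100 treated. An odds ratio for remission and a hazard ratio for SAEs cannot be netted against each other. With no scale declared, a null ratio interaction could be reported as no moderation of harm by age even where the extra events per 100 differ between age groups.

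This is separate from whether the interaction term should contain time. A plain treatment-by-age term in these models raises the same question.

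**Working it through.** **Inputs from the Protocol power table (section H2).** Step 1: 500 per arm, alpha .05/3. SAE: 4% baseline, detectable increase 5.0 points at 80% power. Falls: 20% baseline, 8.8 points. Remission: 40%, 10.2 points. Equal age strata give 250 per arm per age group. At the revised size (SAP 3.3), 708 − 123 = 585 enter Step 1, or 585/6 = 97.5 per cell if evenly split.

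**Reproducing the plan's figures.** Two-proportion power at n = 500 per arm and two-sided .05/3 is 0.793 (SAE), 0.802 (falls) and 0.803 (remission), against a stated .8. The main-effect table is therefore on the absolute scale and reproduces.

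**The remission scenario for HT-1 (13 points versus 0).** Taking 53% versus 40% in the younger group and 40% versus 40% in the older, the odds ratios are 1.69 and 1.00. A zero difference is null on every scale, so the two scales agree in sign and nearly in power: 0.55 for the risk-difference contrast and 0.53 for the logit contrast (250 per cell, two-sided .05). Neither reaches the stated figure above 85%, but that is a different issue.

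**Assumption.** The documents give no event rates by age. The age-specific control rates below are assumed, chosen to average to 4% or 20%.

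**SAE with a constant hazard ratio.** The calculation uses first events under proportional hazards, as a stand-in for the recurrent-event model.
- The HR that takes 4% to 9% is ln(1 − .09)/ln(1 − .04) = 2.31.
- Treated risk = 1 − (1 − p)^2.31.

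| Assumed control rates (<70 / >70) | Treated risks | Excess per 100 | Interaction HR |
|---|---|---|---|
| 2% / 6% | 4.6% / 13.3% | 2.6 / 7.3 | 1.00 |
| 3% / 5% | 6.8% / 11.2% | 3.8 / 6.2 | 1.00 |

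**Falls with a constant absolute excess of 8.8 points.**
- Younger, 10% to 18.8%: OR = (.188/.812)/(.10/.90) = 2.08.
- Older, 30% to 38.8%: OR = (.388/.612)/(.30/.70) = 1.48.
- Ratio = 1.48/2.08 = 0.71, although the absolute excess is the same in both groups.

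**Growing excess with the ratio reversed.** SAE 2% to 6% (younger) and 6% to 12% (older): the excess rises from 4 to 6 points while the OR falls from 3.13 to 2.14 and the HR from 3.06 to 2.07.

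**A case where the scales agree.** Falls 15% to 21.8% and 25% to 35.8%: the excess rises from 6.8 to 10.8 points and the OR from 1.58 to 1.67.

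**Precision (normal approximation, two-sided .05).** For SAE at 2%/6% with HR 2.31, the difference in risk differences is 7.3 − 2.6, about 4.8 points before rounding. Its standard error is 3.1 points at 250 per cell and 4.9 at 97.5, so power is about 34% and 16%. At 3%/5% it is about 12% and 7%. In the falls case above, the logit interaction is significantly negative about 18% of the time at 250 per cell and 10% at 97.5. In the reversed SAE case the logit estimate is negative about 73% of the time at 250 per cell, and significantly so about 9%.

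**The case against.** A reader might infer that HT-1 is worded and powered as a change in absolute differences, so that the planned test contradicts its own hypothesis. The documents do not support that:
- The text says only differences, and elsewhere speaks of relative benefits and risks. Relative may just mean comparative, but nothing commits HT-1 to an additive scale.
- HT-1 has no power scenario for any safety outcome.
- The one binary scenario it has, 13 points versus none, does not depend on scale.

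A reader might also infer that growing harm will be reported with the wrong sign. That depends on the age gradient. Some gradients agree on both scales, and a significant reversal is uncommon in the cases worked here.

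Three further objections carry weight. Applying the interaction to logit and Cox models is a reading, since the text says linear models and the remission model has no time factor; the stated coverage of both benefits and risks makes the reading reasonable. The SAP treats HT-1 as exploratory, and a ratio-scale interaction is conventional. The remission model already contains age by treatment, so age-specific probabilities could be derived from it.

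What remains is that no scale is declared and no age-specific risk difference is planned. The general promise of intervals in SAP 3.4 names no estimand, scale or subgroup.

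**Conclusion.** The point holds as a gap in specification, and closing it is a cheap improvement. HT-1 speaks of differences without declaring a scale, while the interaction for remission, SAEs, falls and injuries would be estimated as a ratio of odds or hazard ratios. Well-being is unaffected because its model is linear.

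Under the assumed age gradients, a null ratio interaction is compatible with an SAE excess 1.6 times as large in the older group (6.2/3.8) or 2.8 times as large (7.3/2.6). An equal fall excess can appear as a ratio of 0.71. These sizes rest on age-specific rates that the documents do not give and on a first-event approximation. They show what can happen, not what is expected.

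Changing scale would not rescue power, which is low either way and lower at the revised sample size. The gain is an interpretable estimate with an interval. Requiring the HT-1 conclusion to rest on the absolute contrast alone would be a preference, and the documents do not compel it.

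**What to change.** In SAP 6.2, under hypothesis 3:
1. Keep the ratio-scale treatment-by-age interaction for H1b, H2a and H2b, and state that this is its scale.
2. Add, from the same fitted models, the risks by arm and age group: remission risk and fall and injury risk at step end, and SAE cumulative incidence or mean cumulative count at a fixed, named time.
3. Report the arm risk differences within each age group and the between-age-group difference in those risk differences, with confidence intervals (delta method or bootstrap).
4. Present both scales side by side. State that harm will not be described as unmoderated by age, or as shrinking with age, from the ratio interaction alone.

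The cost is SAP wording and modest extra programming, with no new data. The downside is more exploratory estimates, with wide intervals at the reduced sample size: about ±10 points for the SAE contrast at 97.5 per cell (1.96 × 4.9).
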